13.2.2. Pregnancy Testing

All women of childbearing potential will have a serum pregnancy test at the screening visit and urine pregnancy tests (UPTs) at Baseline, Week 4, Week 8, Week 12, Week 16, Week 20, Week 24, Early Termination visit, and Week 32/Follow-up. Pregnancy test results must be available prior to the administration of the study drug.

All test results including Tests not done will be summarized by visit on the Safety population.

All confirmed pregnancy test results together with the premenses status and childbearing potential assessment results will be listed on the Safety population.

13.2.3. Virology and TB Testing

Virology including HBsAg, HBcAb, hepatitis C, human immunodeficiency virus 1, and human immunodeficiency virus 2 antibodies will be assessed at the screening visit. Subjects with a positive HBcAb and a negative HBsAg will also be assessed for hepatitis B surface antibody. Subjects with positive HCV antibodies will have a confirmatory test for HCV (e.g., PCR). All virology and genomics results will be listed on the Safety population. All Immunoglobulin E results will also be listed on the Safety population.

Subjects will be assessed for TB infection with a QuantiFERON-TB Gold test at the screening visit. All TB test results will be listed on the Safety population.

13.3. Vital Signs

Vital signs will include pulse rate, systolic and diastolic blood pressure (after the subject has been sitting for at least 5 minutes) and body temperature.

Vital signs will be collected at the Screening visit and at Baseline/Day 1, Week 4, Week 8, Week 12, Week 16, Week 20, Week 24, Early Termination visit, and at Week 32/Follow-up.

Height and weight will be measured at Screening for all subjects. Weight assessments will be conducted at Baseline/Day 1, Week 12, Week 24 and Early Termination.

All vital signs including height and weight (absolute values and change from Baseline) will be summarized as continuous (Baseline and scheduled visits only). Last post-Baseline results (including unscheduled visits in the derivation) will also be included.

The number and percentage of subjects who met criteria of potential CS value ([Section 21.4](#)) for vital signs and weight will be summarized (Baseline and scheduled visits only). Last post-Baseline results (including unscheduled visits in the derivation) will also be included.

Distribution of pulse rate, systolic and diastolic blood pressure will be displayed graphically as boxplot by treatment group for Baseline and each scheduled visit and maximum post-Baseline (including unscheduled visits in the derivation) values.

This document is confidential.

By-subject listing of subjects with potentially CS vital signs and weight will be provided.

All vital signs results will be listed on the Safety population.

13.4. ECG

A 12-lead electrocardiogram (ECG) will be performed and read centrally at Screening, Baseline/Day 1, Week 24 and Early Termination visit.

All ECG data (absolute values and change from Baseline) will be summarized as continuous variables by visit (Baseline and scheduled visits only). All parameters will be presented in alphabetically order.

The overall results of the ECGs recorded as 'Normal', 'Abnormal, NCS' or 'Abnormal, CS' will be summarized by treatment group and visit (scheduled visits only). Clinical significance will be determined by the investigator.

Additionally all ECG findings will be summarized with numbers and percentages by visit (Baseline and scheduled visits only).

All ECG results will be listed on the Safety population.

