4.3. Determination of Sample Size

In order to achieve at least 90% power for both primary endpoints at 5% significance level, 270 (180 Nemolizumab, 90 placebo) subjects will be randomized to detect the following differences in both primary

This document is confidential.

endpoints between treatment groups with 2:1 randomization, assuming a 15% dropout rate during treatment period.

NRS responders (≥ 4 point reduction from baseline): Based on phase 2a data, it is expected that the NRS response at Week 16 would be 50% in Nemolizumab and 20% in placebo.

IGA response (0/1): It is expected that the IGA response at Week 16 would be 30% in Nemolizumab and 10% in placebo.

Table 4-1 provides the resulting power with 270 subjects (180 Nemolizumab, 90 placebo) for different responses in primary endpoints.

Table 4-1: Results of Power Analysis

Endpoint	Placebo	Nemolizumab	Power at 5% significance level (N= 270 [180 Nemolizumab, 90 placebo])
IGA responder	10%	30%	90%
	10%	27%	83%
	10%	25%	77%
PP-NRS Responder	20%	50%	> 90%
	20%	45%	> 90%
	20%	40%	84%
Assuming 15% attrition rate during treatment period. Based on continuity corrected Chi-square test.			

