8.4. Visit Windows

Efficacy by-visit summaries will use the analysis visit. All visits (Scheduled, Unscheduled and early termination visits) will be windowed based on the analysis visit window in [Table 8-1](#) which is based on study day. If multiple measurements are taken within the same window, the one taken closest to the target study day will be used for the analysis. If there are multiple measurements with same difference from target day, the later assessment should be used for the analysis.

Table 8-1: Analysis Visit Window

Analysis Visit	Target Study Day	Visit Window for IGA, PAS, PN associated Pain frequency and intensity	Visit Window for PGIS-P, PGIS-SD, PGIC-P, PGIC-SD, PGAD, PGAT, EQ-5D, HADS	Visit Window for DLQI
Baseline	1	≤ 1	≤ 1	≤ 1
Week 1	8	NA	2 to 60	NA
Week 4	29	2 to 42	NA	2 to 60
Week 8	57	43 to 70	NA	NA
Week 12	85	71 to 98	NA	NA
Week 16	113	99 to 126	61 to 154	61 to 154
Week 20	141	127 to 154	NA	NA
Week 24	169	155 to 210	155 to 210	155 to 210

This document is confidential.

Week 32 Follow-up	225	211 to 238	NA	NA
-------------------	-----	------------	----	----

All daily diary efficacy data will be classified into analysis visits as described in [Table 8-2](#) considering the data during the 7 days immediately preceding the target day of analysis visit.

Analysis visit of diary (ePRO) data will be defined depending on the data collection as below.

Diary data assessed within the extended timeframe below will be considered for analysis. The following rule will be applied for post-treatment assessments only.

- Evening assessment (PP/AP NRS) recorded from 17:00:00 to 00:59:59
- Morning assessment (SD NRS, morning sleep diary) recorded from 5:00:00 to 17:59:59

Consecutive daily assessment:

For the evening assessments (PP NRS, AP NRS), the daily data collected up to Week 24 will be classified into analysis visits considering the data during the 7 days immediately preceding the target study day of analysis visit. Similarly, for the morning assessment (SD NRS, morning sleep diary), the 7 days data up to the target study day will be classified into analysis visit. Details of the analysis visit window are in Table 8-2 below.

Table 8-2: Analysis Visit Window for Evening and Morning Assessments*

Analysis Visit	Target Study Day of Analysis Visit	Visit Window for evening assessment (PP NRS, AP NRS)	Visit Window for morning assessment (SD NRS, morning sleep diary)
Baseline ^a	1	-7 to -1	-6 to 1 before dosing
Week 1	8	1 to 7	2 to 8

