Week 2	15	8 to 14	9 to 15
Week 3	22	15 to 21	16 to 22
Week 4	29	22 to 28	23 to 29
Week 5	36	29 to 35	30 to 36
Week 6	43	36 to 42	37 to 43
Week 7	50	43 to 49	44 to 50
Week 8	57	50 to 56	51 to 57
Week 9	64	57 to 63	58 to 64
Week 10	71	64 to 70	65 to 71
Week 11	78	71 to 77	72 to 78
Week 12	85	78 to 84	79 to 85
Week 13	92	85 to 91	86 to 92
Week 14	99	92 to 98	93 to 99
Week 15	106	99 to 105	100 to 106
Week 16 ^b	113	106 to 112	107 to 113
Week 17	120	113 to 119	114 to 120
Week 18	127	120 to 126	121 to 127
Week 19	134	127 to 133	128 to 134
Week 20	141	134 to 140	135 to 141
Week 21	148	141 to 147	142 to 148
Week 22	155	148 to 154	149 to 155
Week 23	162	155 to 161	156 to 162

This document is confidential.

Week 24	169	162 to 168	163 to 169
---------	-----	------------	------------

^a If there are less than 4 non-missing assessments within last 7 days prior to the first dose, the interval lower bound will be extended up to 7 additional days, one day at a time, to obtain the most recent 4 non-missing values. The extension will not be applied for the sensitivity analysis by using a minimum of 2 (or 3) daily scores out of the 7 days.

^b If there are less than 4 assessments during Week 16 visit window, upper bound of the visit window (106 - 112) or (107 - 113) will be extended for 5 additional days. If there are still less than 4 assessments after extending upper bound of the visit window, lower bound of the visit window will be extended for another 5 days until 4 assessments are reached.

* For diary data, if the intake date of rescue therapy is before and on the last day of the weekly visit window, this week will be treated as treatment failure except for OC analysis and the weekly average will be imputed using the worst case value, see [Section 8.3](#). For MMRM analysis, values will be considered as missing.

Safety and pharmacokinetics data will not be windowed for by-visit summary. i.e., scheduled visit data will be used for analysis.

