13.2. Laboratory Evaluations

13.2.1. Clinical Laboratory Evaluations

The hematology laboratory analyses, clinical chemistry laboratory analyses, and urinalyses will be performed at a central laboratory. Reference ranges will be supplied by the central laboratory and used by the investigator to assess the laboratory data for clinical significance and pathological changes. Reference ranges will be provided in the laboratory manual.

This document is confidential.

The following parameters will be reported for laboratory data.

- **Hematology:** Hemoglobin, hematocrit, white blood cell (WBC) count (with differential including eosinophils), red blood cell (RBC) count, platelet count, and mean cell volume (MCV).
- **Chemistry:** Creatinine, aspartate aminotransferase (AST), alanine aminotransferase (ALT), gamma glutamyltransferase (GGT), alkaline phosphatase, lactate dehydrogenase (LDH), total bilirubin, direct bilirubin, creatinine phosphokinase ([CPK], CPK isoenzyme test will be performed only if CPK is elevated to $> 2.5 \times \text{ULN}$), albumin, total protein, uric acid, sodium, potassium, calcium, chloride, glucose, urea, total cholesterol, triglycerides, low-density lipoprotein (LDL), and high-density lipoprotein (HDL). Follicle-stimulating hormone (FSH) will be collected for postmenopausal subjects.
- **Urinalysis:** pH, glucose, ketones, blood, protein, leukocytes, nitrites, bilirubin, urobilinogen, and specific gravity.

Laboratory assessments are performed at Screening, Baseline/Day 1, Week 4, Week 8, Week 16, Week 24, Early Termination and Week 32/Follow-up.

Hematology and chemistry laboratory data (absolute values and change from Baseline) will be summarized as continuous variables by visit (Baseline and scheduled visits only). Urinalysis laboratory data will be summarized by visit (Baseline and scheduled visits only). Last post-baseline, worst post-baseline and maximum post-baseline results will also be included in the summaries and will include unscheduled visits in the derivation. Worst post-baseline value will be defined as the highest or lowest value relative to the reference range. Parameters will be presented in alphabetically order.

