13.6.2. Peak Expiratory Flow

Peak expiratory flow (PEF) testing during the clinical study will be performed under the supervision of qualified study personnel. Peak expiratory flow measurements should consist of 3 good efforts, with the best result documented. Obtained PEF values will be compared to predicted values based on the subject's age, sex and height.

PEF testing will be performed for all subjects at screening, Baseline/Day 1, Week 8, Week 16, Week 24, Early Termination, and Week 32/Follow-up visits. For subjects reporting a medical history of asthma, PEF testing will be performed at all visits during the clinical study. For subjects diagnosed with de novo asthma, PEF testing will be performed at all visits, starting with the visit in which the diagnosis was confirmed.

Following PEF parameters will be summarized as a continuous variable (Baseline and scheduled visits only):

- Actual peak expiratory flow rate
- Predicted peak expiratory flow rate
- Actual PEF of predicted value (%).

These PEF parameters will be summarized separately for the subset of subjects with and without history of asthma.

The number and percentage of subjects with PEF < 80% of predicted value will be summarized by treatment group, visit (baseline and scheduled visits only), and medical history of asthma (with and without history of asthma).

All PEF results will be listed on the Safety population.

This document is confidential.

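### ECG, PEF and ACT summaries exclude unscheduled readings, have no last or worst post-baseline row, and leave the handling of early termination readings unstated

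*SAP*

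**What the plan says.** Section 13.4 fixes the ECG collection points: "A 12-lead electrocardiogram (ECG) will be performed and read centrally at Screening, Baseline/Day 1, Week 24 and Early Termination visit". Three ECG summaries follow (continuous values, overall interpretation, findings). All are limited to scheduled visits, with baseline added for the first and third. For the continuous values the wording is: "All ECG data (absolute values and change from Baseline) will be summarized as continuous variables by visit (Baseline and scheduled visits only").

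Section 13.6.2 has the same limit for PEF: "Following PEF parameters will be summarized as a continuous variable (Baseline and scheduled visits only"). It repeats the limit for the count of subjects below 80% of predicted. Section 13.6.3 applies it to the ACT score and to the count with ACT of 19 or less.

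Section 8.4 sets the general rule: "Safety and pharmacokinetics data will not be windowed for by-visit summary. i.e., scheduled visit data will be used for analysis". Earlier in the same section, in the text on efficacy by-visit summaries, three visit types are named: "All visits (Scheduled, Unscheduled and early termination visits) will be windowed".

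Laboratory data are handled differently in section 13.2.1: "Last post-baseline, worst post-baseline and maximum post-baseline results will also be included in the summaries and will include unscheduled visits in the derivation". Section 13.3 gives vital signs a last post-baseline row on the same basis.

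**The concern.** Unscheduled visits are where a reading prompted by symptoms would be taken, and the ET visit is where a subject leaving the study is last measured. If neither feeds a summary, the ECG, PEF and ACT tables describe only subjects who were still attending, on planned days. Newly diagnosed or worsening asthma is an adverse event of special interest (AESI) in section 13.1, and asthma events are adjudicated, so measured lung function is of real interest here.

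The planned tables cannot give, by arm, the number of subjects who ever had a PEF below 80% of predicted, ever had an ACT of 19 or less, or ever had an abnormal post-baseline ECG. The listings hold the readings, but a listing makes no comparison between arms. The laboratory section solves this problem within the same chapter, and no reason is given for treating ECG, PEF and ACT otherwise.

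**Working it through.** **Which readings can reach a summary table**

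| Data | Planned post-baseline collection | Visits summarized | Derived post-baseline row |
|---|---|---|---|
| Laboratory (13.2.1) | Weeks 4, 8, 16, 24, ET, Week 32 | baseline and scheduled | last, worst, maximum; unscheduled included |
| Vital signs (13.3) | Weeks 4 to 24 every 4 weeks, ET, Week 32 | baseline and scheduled | last; unscheduled included |
| ECG (13.4) | Week 24, ET | scheduled (baseline in two of three) | none |
| PEF (13.6.2) | Weeks 8, 16, 24, ET, Week 32; every visit with asthma | baseline and scheduled | none |
| ACT (13.6.3), asthma only | Weeks 4 to 24 every 4 weeks, ET, Week 32 | scheduled (baseline for the score) | none |

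Table 4-2 also allows ECG, PEF and ACT at unscheduled visits.

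The indexes recover nothing. ECG tables 14.3.4.3.1 to 14.3.4.3.3, PEF and ACT tables 14.3.4.4.4 to 14.3.4.4.11 and the figures in section 19 contain no last, worst or maximum output for these measures. The readings appear in listings 16.2.8.2.2 (ECG), 16.2.8.2.5 (PEF), 16.2.8.2.7 (ACT) and 16.2.8.2.8 (falls of at least 15% in PEF or ACT). Section 21.4 sets potentially clinically significant (PCS) ranges for hematology, chemistry and vital signs but none for ECG, so no threshold table catches an ECG reading either.

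**Unscheduled visits.** The exclusion is explicit, because the summaries are restricted to scheduled visits and nothing brings unscheduled readings back in.

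**Early termination.** The SAP does not define a scheduled visit for the safety tables. Two readings are open:

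- Under the three visit types in 8.4, ET is distinct from scheduled and would be left out.
- ET has its own column in Table 4-2 and is listed as a planned collection point in 13.4, 13.6.2 and 13.6.3, so a programmer could show it as a nominal visit.

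**Scale for ECG under the first reading.** The SAP states no figure of its own for this. Inputs from section 4.3 are 180 nemolizumab, 90 placebo and a 15% dropout rate, worded as "assuming a 15% dropout rate during treatment period".

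- Nemolizumab: 0.15 × 180 = 27
- Placebo: 0.15 × 90 = 13.5
- Total: 0.15 × 270 = 40.5, about 40 of 270

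For these subjects the ET ECG would be the only planned post-baseline ECG, since none is scheduled before Week 24 or at Week 32. Over an assumed dropout range of 5% to 20%, the total runs from 0.05 × 270 = 13.5 to 0.20 × 270 = 54.

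The figure does not carry over to PEF or ACT. Early leavers may already have scheduled readings, from Week 8 for PEF and from Week 4 for ACT in subjects with asthma.

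**The case against.** A reader might infer that ET readings certainly never reach a table. The text does not support that. The three visit types come from the efficacy windowing rule, whereas the safety chapter contrasts only scheduled with unscheduled visits. Even the laboratory wording adds back unscheduled visits without naming ET. For ET the SAP is ambiguous, not explicit. The ambiguity still needs settling, and showing ET as its own row would still not give a last or worst value per subject.

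A reader might also take 40 of 270 as an expected loss. It is an upper illustration. The 15% is a planning assumption, section 4.1 asks subjects who stop study drug to return for all remaining visits, and not every subject who leaves the study will have an ET ECG. Stopping drug for an adverse event is therefore not the same as missing the Week 24 ECG.

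A third inference is that the tables are biased towards no effect. That is plausible, but nothing in the SAP shows that the excluded readings are worse or differ by arm. By-visit tables restricted to planned days also avoid symptom-triggered measurement, which is a legitimate reason for that format.

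Nor would an asthma episode go uncompared. AESI and adjudication tables are by arm, and section 13.6.1 summarizes answers on new or worsening asthma, wheeze, dyspnea and cough since the last visit. This stands, but those outputs count reported events and answers, not measured lung function.

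For vital signs, section 13.3 plans by-arm boxplots of maximum post-baseline pulse and blood pressure that include unscheduled visits. High excursions are therefore displayed. Low excursions, and any excursion that is not the last reading, can still be missing from the PCS count.

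**Conclusion.** The point holds as a reporting gap in the safety tables. Unscheduled ECG, PEF and ACT readings reach listings only, and no last or worst post-baseline row exists for these measures. Whether ET readings are also left out depends on a term that the SAP does not define. If they are, the effect is largest for ECG: up to about 40 of 270 subjects at 15% dropout, or about 14 to 54 over an assumed 5% to 20%. Those counts assume that every dropout leaves before Week 24 and has an ET ECG, so the true number would be smaller.

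No efficacy result is affected, and no direction of bias is established. The change is worth making because the data are already collected and the laboratory section already uses the method.

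**What to change.** - **Sections 13.4, 13.6.2 and 13.6.3:** add last and worst post-baseline rows by arm. The worst-value rows are worst ECG interpretation, lowest PEF as a percentage of predicted and any PEF below 80%, and lowest ACT and any ACT of 19 or less. Derive them from all post-baseline records, naming both ET and unscheduled visits. Copying the laboratory wording alone would leave ET unsettled.
- **Section 8.4:** state how ET is handled in by-visit safety tables.
- **Section 13.3 (minor):** add an any-post-baseline row to the vital-sign PCS table, since the maximum-value boxplots do not show low excursions.

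The cost is SAP wording and a few rows in planned tables, with no new data. Worst-value rows partly reflect measurement triggered by symptoms, so they should be read alongside the by-visit tables and not in place of them.

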13.5. Physical Examination

Following body system assessments will be performed at Screening, Baseline/Day 1, Week 8, Week 16, Week 24, Early Termination, and Week 32/Follow-up:

- Head, ears, eyes, nose, throat, neck (including thyroid),
- Skin/integumentary system,
- Cardiovascular system,
- Respiratory system,
- Gastrointestinal system,
- Musculoskeletal system,
- Lymph nodes,
- Nervous system, and
- Extremities.

The number and percentage of subjects with physical examination results by body system classified as 'Normal', 'Abnormal, NCS' or 'Abnormal, CS' will be summarized (Baseline and scheduled visits only).

Shift from Baseline of the physical examination category will also be summarized by body system and by visit.

By-subject listing will be provided for subjects who have at least one abnormal result from any body system or who missed the assessment due to any reason.

This document is confidential.

All physical examination results will be listed on the Safety population.

13.6. Respiratory Assessments

13.6.1. Respiratory Examination

A respiratory examination consists of medical interview. Questions regarding medical history of asthma, wheeze, dyspnea, and cough, will be performed for all subjects at Screening. At Baseline/Day 1, Week 4, Week 8, Week 12, Week 16, Week 20, Week 24, Early Termination and Week 32/Follow-up questions are asked regarding:

- newly diagnosed (de novo) with Asthma / experience a worsening of Asthma since last visit
- newly diagnosed with Wheeze since last visit / experience a worsening of Wheeze since last visit
- newly diagnosed with Dyspnea since last visit / experience a worsening of Dyspnea since last visit
- newly diagnosed with Cough since last visit / experience a worsening of Cough since last visit

Newly diagnosed asthma or unexpected worsening of asthma are also reported as AESI. All Respiratory examination questionnaire results will be summarized with numbers and percentages by visit and listed on the Safety population.

13.6.2. Peak Expiratory Flow

Peak expiratory flow (PEF) testing during the clinical study will be performed under the supervision of qualified study personnel. Peak expiratory flow measurements should consist of 3 good efforts, with the best result documented. Obtained PEF values will be compared to predicted values based on the subject's age, sex and height.

PEF testing will be performed for all subjects at screening, Baseline/Day 1, Week 8, Week 16, Week 24, Early Termination, and Week 32/Follow-up visits. For subjects reporting a medical history of asthma, PEF testing will be performed at all visits during the clinical study. For subjects diagnosed with de novo asthma, PEF testing will be performed at all visits, starting with the visit in which the diagnosis was confirmed.

Following PEF parameters will be summarized as a continuous variable (Baseline and scheduled visits only):

- Actual peak expiratory flow rate
- Predicted peak expiratory flow rate
- Actual PEF of predicted value (%).

These PEF parameters will be summarized separately for the subset of subjects with and without history of asthma.

The number and percentage of subjects with PEF < 80% of predicted value will be summarized by treatment group, visit (baseline and scheduled visits only), and medical history of asthma (with and without history of asthma).

All PEF results will be listed on the Safety population.

This document is confidential.

